### **3 Introduction**

This Statistical Analysis Plan (SAP) is based on the current trial protocol (version 5, Final 18 January 2017). Where statistical methods differ substantially between this SAP and the protocol, the differences will be identified in the SAP.

This SAP describes the datasets and the statistical methods to be used for the reporting and analysis of all data collected in Part 2 (cohorts 9 and 10), except for the 12-lead ECG continuous monitoring data which will be analysed by iCardiac Ltd (or an alternative provider), if applicable.

The randomisation code will not be broken before this SAP is finalised and signed. If a future protocol amendment necessitates a substantial change to the statistical analysis of the trial data, this SAP will be amended accordingly. If, after database lock, additional analyses are required to supplement the planned analyses described in this SAP, those unplanned analyses will not be described in an amended SAP, but they will be identified in the integrated clinical trial report (CTR). Any deviations from this SAP will be documented in the CTR.

This SAP has been written in consideration of the following guidelines:

- International Conference on Harmonization (ICH) E9, Guidance for Industry: Statistical Principles for Clinical Trials (ICH E9 1998); and
- ICH E3, Guidance for Industry: Structure and Content of Clinical Study Reports (ICH E3 1995).

Pharmacokinetic analysis will be done using WinNonlin v6.3 on a Windows PC. Statistical analysis will be done using SAS® 9.3 on a Windows PC.

## **4 Study Objective(s) and Endpoint(s)**

### **4.1 Study Objective(s)**

#### **4.1.1 Primary Objective(s)**

- To investigate the safety and tolerability of emodepside (BAY 44-4400) after single oral doses administered as solution or immediate release (IR) tablets in healthy male subjects.

#### 4.1.2 Secondary Objective(s)

- To investigate the pharmacokinetics (PK) of emodepside (BAY 44-4400), after administration as oral solution, and IR tablet (optional)
- To conduct an exploratory investigation of the relative bioavailability of the 5 mg and 20 mg IR tablet formulation using data generated in this study (optional)
- Possibility to determine the effect of food on the bioavailability of emodepside (BAY 44-4400) after single oral doses administered as solution or IR tablets.

#### 4.2 Study Endpoint(s)

##### 4.2.1 Safety and Tolerability Variables:

- Adverse Events (AEs).
- Physical and Neurological examination findings (including assessments of alertness, speech, language, and comprehension; cranial nerves; motor exam; coordination/cerebellar function; tremor of the hands, legs and head (postural, kinetic and rest tremor); sensation; and gait and postural stability (Pull test); mood; and sleepiness.).
- Vital signs: heart rate (HR), systolic and diastolic blood pressure (BP) in supine and sitting position (Cohort 10 only in supine), weight, body mass index (BMI; height at screening only), oral temperature.
- 12-lead ECG (HR, PR, QRS, QTcF), and for selected cohorts 12-lead ECG continuous recording (for emodepside exposure response analysis - HR, PR, QRS and QTcF).
- Clinical laboratory parameters:
  - Hematology: hemoglobin, hematocrit, MCV, MCH, MCHC, platelets, reticulocytes, white blood cells (WBC) differential, red blood cells (RBC), glycated haemoglobin (HbA1C) (at screening);
  - Coagulation: activated partial thromboplastin time (aPTT), prothrombin time (PT);
- Biochemistry: aspartate aminotransferase (AST), alanine aminotransferase (ALT), alkaline phosphatase (AP), glutamate dehydrogenase (GLDH), gamma-glutamyl transpeptidase (GGT), LDH, CK, amylase, lipase, free T4 and T3, thyroid-stimulating hormone (TSH), glucose, cholesterol (high-density lipoprotein [HDL], and low-density lipoprotein [LDL], total), triglycerides, creatinine, urea, uric acid, bilirubin (total and conjugated), total protein, sodium, potassium, calcium, chloride and magnesium in serum;

- Urinalysis: by dipstick - glucose, ketone bodies, specific gravity, occult blood, pH, proteins, leucocytes, bilirubin, urobilinogen, nitrites.
- Ophthalmological assessments (Cohort 10 only)

#### 4.2.2 Pharmacokinetic Variables:

Based on the plasma concentration time data, the following PK parameters of emodepside will be calculated.

- Main PK parameters:  $AUC_{\infty}$ ,  $AUC_{\infty}/D$ ,  $C_{max}$ ,  $C_{max}/D$ , of emodepside (BAY 44-4400)
- Exploratory PK parameters:  $C_{max,norm}$ ,  $T_{max}$ ,  $t_{1/2}$ , MRT, CL/F,  $AUC_{\infty,norm}$ ,  $AUC_t$ ,  $AUC_{t,norm}$ ,  $V_z/F$  of emodepside (BAY 44-4400)
- Other parameters:  $\lambda_z$ ,  $AUC_{t-\infty}$ , points terminal

The following PK parameters of metabolites of emodepside may be calculated:

$AUC_{\infty}$ ,  $AUC_{\infty}/D$ ,  $C_{max}$ ,  $C_{max}/D$ ,  $C_{max,norm}$ ,  $T_{max}$ ,  $T_{1/2}$ ,  $AUC_{\infty,norm}$ ,  $AUC_t$ ,  $AUC_{t,norm}$

In urine, the amount and concentration of emodepside and possibly its metabolites will be measured. The appropriate specific PK parameters to be calculated will be decided according to the concentration.

#### 4.2.3 Pharmacodynamic Variables:

- Profiles of glucose and insulin, glucagon and cortisol (Cohort 9 only), only on Pre-Day (Day -1), Profile Day (Day 0), and Day 1.
- Single samples of prolactin and leptin, only on Pre-Day (Day -1), Profile Day (Day 0), and Day 1 (Cohort 9 only).

### 4.3 Statistical Hypotheses

No formal statistical testing will be done.

## 5 Study Design

This is a single-center, blinded, randomised, placebo-controlled, parallel-group, single-dose, 2-cohort, dose-escalation, comparison study investigating safety, tolerability, and PK of

emodepside, after administration as an oral liquid service formulation (LSF) solution in healthy male subjects. Within each cohort, subjects will be randomised to receive either emodepside or placebo (n=8 per cohort; 6 assigned to emodepside and 2 assigned to placebo).

Subjects in Cohort 9 will receive 10mg solution of emodepside or matching placebo in a fed state and subjects in Cohort 10 will receive 40mg solution of emodepside in fasted state.

CONFIDENTIAL

- c: Height at screening only, for calculation of BMI. Weight at screening for calculation of BMI, also at -24h (Day -1) for PK calculations.
- d: Neurological examination designed for the study, see Protocol Section 8.19.4 and Study Procedures Manual
- e: Administration of study drug while fasting or after a high-calorie, high-fat breakfast
- f: To include 3 repeat ECGs at these timepoints, with a time difference of about 1 minute, and single recordings at other timepoints
- g: For selected cohorts in Part 1 (see Protocol Section 8.19.2 continuous 12-lead ECG recording will be started 1 hour before dosing and continue for 24 hours post-dosing. ECGs will be extracted at predose, at three timepoints (-60, -45, and -30 minutes for fasted subjects or -90, -75, and -60 minutes for fed subjects) and at the timepoints at which PK blood samples are drawn. Subjects will be supine for 10 minutes prior to and 5 minutes after each nominal timepoint. When ECG extraction coincide with safety ECGs, vital signs and blood draws, procedures will be performed in said order.
- h: Vital signs to include BP (supine; plus sitting BP at the indicated timepointshi) and HR. Oral temperature only at screening and -24h.
- i: Adverse Event (AE) monitoring will be throughout the study (spontaneous and solicited) to include questioning for tolerability and safety, however at these indicated timepoints will be specific questioning about AEs.
- j: In addition to the PK sample, metabolite samples are collected only for the indicated time points ji. As an option, at the sponsor's discretion, an additional sample of no more than 1mL may be taken at each PK timepoint from all subjects in up to 2 cohorts.
- k: Start and end of urine collection for each bottle are indicated as hours post drug..
- l: Hematology, Coagulation, Chemistry; Urinalysis by dip stick.
- m: At Screening only: HIV 1, 2, Hepatitis B, C, HbA1C, in addition to hematology, coagulation, urinalysis, and chemistry.

**Table 2. Follow-Up after Day 7 – Schedule Options 1, 2, or 3 Depending on Emodepside Plasma Concentrations at Day 7 in Previous Cohort(s) (from Cohort 5 onwards), Respectively.**

For Screening and Days -2 through Day 8 see Table 1

OPTION 1		Out-Patient Phase				Follow-Up Visit at 3 weeks (+3 days) post-dose
Day	Discharge on Day 7					
Physical Examination						(see Table 1)
Neurological Examination						(see Table 1)
12-lead ECG						(see Table 1)
Vital signs n						(see Table 1)
Adverse event monitoring l						(see Table 1)
PK in plasma						(see Table 1)
Laboratory Safety l,m						(see Table 1)
OPTION 2		Out-Patient Phase				Follow-Up Visit at 3 weeks (+3 days) post-dose
Day	Up to 4 visits during the period from Day 8–21 inclusive (as needed)					
	Ambulatory Evaluation Visits, Scheduled As Needed					
Physical Examination						(see Table 1)
Neurological Examination						(see Table 1)
12-lead ECG						(see Table 1)
Vital signs n						(see Table 1)
Adverse event monitoring l	X		X	X	X	(see Table 1)
PK in plasma	X		X	X	X	(see Table 1)
Laboratory Safety l,m	X		X	X	X	(see Table 1)
OPTION 3		Discharge from Ward on Day X				Follow-Up Visit at 3 weeks (+3 days) post-dose
Day	8 (±1) (as needed)	10 (±1) (as needed)	12 (±2) (as needed)	14 (±2) (max.)		
	Prolonged In-House Evaluation Phase with Discharge from Ward on Day X (8-14)					
Physical Examination						(see Table 1)
Neurological Examination						(see Table 1)
12-lead ECG						(see Table 1)
Vital signs n						(see Table 1)
Adverse event monitoring l	X	X	X	X		(see Table 1)
PK in plasma	X	X	X	X		(see Table 1)
Laboratory Safety l,m	X	X	X	X		(see Table 1)

(dosing Day)

- a Including a 10-minute supine phase before supine BP, HR, body temperature, ECG; and also recommended before drawing blood samples.
  - b Height at screening only, for calculation of BMI. Weight at screening for calculation of BMI, also at -24h (Day -1) for PK calculations.
  - c Neurological examination designed for the study, see Protocol Section 8.19.4 and Study Procedures Manual.
  - d Colour blindness to be determined at Screening visit 1.
  - e If subjects are eligible for study entry based on Screening visit 1 assessments, they will be asked to undergo an ophthalmology exam (Screening visit 2) within a week before Profile Day or on Pre-Day at the latest. All assessments for Screening Visit 1 will be performed prior to Screening Visit 2, but visits can be combined if necessary.
  - f Administration of study drug is in the fasted-state only.
  - g To include 3 repeat ECGs at these timepoints, with a time difference of about 1 minute, and single recordings at other timepoints.
  - h Vital signs to include supine BP and HR. Oral temperature only at screening and -24h.
  - i Adverse Event (AE) monitoring will be throughout the study (spontaneous and solicited) to include questioning for tolerability and safety, however at these indicated timepoints will be specific questioning about AEs.
  - j Timepoint shown as (X) indicates sample will be taken off-site whilst at the ophthalmology clinic. As an option, at the sponsor's discretion, an additional sample of no more than 1 mL may be taken at each PK timepoint from all subjects in up to 3 cohorts.
  - k Hematology, Coagulation, Chemistry; Urinalysis by dip stick.
  - l At Screening only: HIV 1, 2, Hepatitis B, C, HbA1C, in additional to hematology, coagulation, urinalysis, and chemistry.
  - m Ophthalmology exams will be performed on Profile-Day (Day 0) approximately 2-2.5 h post-dose. If deemed necessary by the ophthalmologist additional ophthalmology follow-up visit(s) may be scheduled for eye-related AEs.
-

## 6 Planned Analyses

### 6.1 Interim Analyses

No interim analyses are planned. However, the blinded safety and PK data will be reviewed after Cohort 9.

### 6.2 Final Analysis

The database will be locked once all subjects have completed the study, data have been entered and all queries resolved. The final analysis will be carried out following database lock and unblinding.

## 7 Sample Size Considerations

### 7.1 Sample Size Assumptions

No formal sample size calculations have been performed as this is an exploratory study. A sample size of 8 per cohort will be considered sufficient to examine the safety and tolerability of emodepside as well as the PK after single oral administration of the investigational drug. For evaluation, a minimum number of 6 evaluable subjects per cohort is required.

## 8 Analysis Populations

The following population sets will be identified:

- Safety Population: All subjects who received at least one dose of IMP.
- PK Concentration Population: All subjects who received at least one dose of IMP and for whom a pharmacokinetic sample has been analysed.
- PK Parameter Population: All subjects in the PK Concentration Population for whom pharmacokinetic parameters can be derived.

In all populations, treatment will be assigned based upon the treatment subjects actually received, regardless of the treatment to which they were randomised.

The primary endpoint will be analysed using the safety population.

### 8.1 Analysis Datasets

All analysis datasets will be based on observed data, except as outlined in Section 10.2.

## 9 Treatment Comparisons

The treatment comparison of interest is active (emodepside) versus placebo.

### 9.1 Data Display Treatment and Other Subgroup Descriptors

The sort order for treatment groups will be placebo, then study treatment in ascending dose order.

Listings of data will be sorted and displayed by treatment group, subject number, and also by date and time if applicable.

All subjects in cohorts 9 and 10 receiving the same formulation of placebo will be combined to form a pooled placebo group.

The treatment descriptions to be used on all tables and listings are:

Treatment Groups	Short Description
Placebo [solution](Fed)	PLA [sol](Fed)
Placebo [solution](Fasted)	PLA [sol](Fasted)
Emodepside (xx mg) [solution](Fed)	xx mg [sol](Fed)
Emodepside (xx mg) [solution](Fasted)	xx mg [sol](Fasting)

### **9.1.1 Conventions for Summary Statistics and Data Displays**

The minimum set of summary statistics for numeric variables will be: n, mean, standard deviation (or standard error), median, minimum, and maximum. 95% confidence intervals will be presented where appropriate for data interpretation.

Categorical data will be summarised in frequency tables with n and percentage. Summaries of a categorical variable will include all recorded values.

The minimum and maximum values will be presented with the same number of decimal places as the raw data collected on the CRF (or to 3 significant figures for derived parameters). The mean and percentiles (e.g. median, Q1, and Q3) will be presented using one additional decimal place. The standard deviation and standard error will be presented using two additional decimal places.

Placebo subjects will be pooled across cohorts 9 and 10 taking into account formulation and fed/fasted status.

## **10 Data Handling Conventions**

### **10.1 Premature Withdrawal and Missing Data**

All subjects who withdraw prematurely from the study or study drug will be included in the statistical analyses.

If a subject completes the treatment period but has missing data, then this will be made apparent in the subject listings. Missing data will not be imputed except for as outlined in Section 10.2.

If the study is prematurely discontinued, all available data will be listed and a review will be carried out to assess which statistical analyses are still considered appropriate.

Data collected at unscheduled time points during the study will not be used in the summaries or data analyses. They will be included in the listings.

If time information (i.e. hours and/or minutes) for adverse events or concomitant medication is missing, but the day is present, then the time will be calculated in days. If date information is partial or missing, then any derived times (e.g. AE start time from last study medication) will be listed as missing.

Conventions for handling missing plasma concentrations are given in Appendix B.

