8.11. Follow-Up Visit (3 weeks [+3 Days] after dosing)

Approximately three weeks after their dose the subjects will return to the Phase 1 Unit for a Follow-Up Visit (all cohorts in Parts 1 and 2), and the following procedures will be completed:

- Complete physical examination
- Complete neurological examination
- 12-lead ECGs, as a single reading,
- Blood pressure/heart rate: in supine position,
- AE monitoring (spontaneous and solicited adverse event monitoring will include specific questioning for tolerability and safety), including any concomitant medications (ie, prescription or nonprescription drugs, and dietary supplements) taken during the duration of this study up to the follow-up visit,
- Laboratory safety blood and urine specimens
- PK blood specimens

For Cohort 10 only: If deemed necessary by the ophthalmologist additional ophthalmology follow-up visit(s) may be scheduled to characterize and assess any eye-related AEs.

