8.12. Sampling time points and additional tests

With the sponsor's approval, additional time points may be introduced, and changes to time points may be made, if there is reason to believe that the change might improve the quality of the data (for example, if it is believed that an important effect of the IMP is occurring at a time when no measurements are scheduled), or if extra procedures are needed in the interest of subject safety. However, the total volume of blood taken in the trial will not exceed the value given in Section 8.18, unless in the opinion of the Investigator, it's in the subject's best interest that extra blood is taken for additional safety tests. Any additional urine collections may include continuous, total collections, if necessary. An additional 48 hours' residence in the ward and additional outpatient visits, will be permitted, in the event of a technical failure, and/or if extra observations or samples of blood or urine are needed. Similarly, the interval between outpatient visits (Option 2 only, see Section 8.10) may be changed if data collected during the study support the change.

In the case of any samples for pharmacokinetic analysis, the following will **not** be regarded as protocol deviations:

- 1. deviations of not more than 5 min on measurements scheduled up to and including 4 h after dosing;
- 2. deviations of not more than 15 min on measurements scheduled from after 4 h to 24 h after dosing;
- 3. deviations of not more than 1 h on measurements scheduled more than 24 h after dosing; and
- 4. deviations of not more than 1 or 2 days on measurements scheduled for ambulatory visits in Option 2. Deviations are shown in the schedule of events in Table 4.

For all other procedures, the following will **not** be regarded as protocol deviations:

Table 7. Permitted deviation windows for all other procedures ¹										
TIME F	TIME POINT									
Day –1	Day 0	RELATION TO THE SCHEDULED TIME POINT								
Pre –24 h	Pre-dose (0 h)	Within 75 min before ²								
–24 h to –23.5 h	Up to and including 30 min after dosing	+/– 5 min ²								
After –23.5 h to –20 h	After 30 min to 4 h after dosing ⁵	+/– 10 min ^{2,3}								
After -20 h to -12 h	After 4 h to 24 h after dosing	+/– 15 min ²								
NA	more than 24 h after dosing	+/– 1 hour								
NA	Ambulatory visits in Option 2	1 or 2 days ⁴								

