### **12.5 Clinical Laboratory Evaluations**

Haematology, clinical chemistry and urinalysis evaluation at each planned assessment, and change from baseline at each planned post-baseline assessment, will be summarised by actual treatment.

Urinalysis parameters will also be listed.

All laboratory values of potential clinical importance will be listed and all related laboratory results (i.e. haematology or clinical chemistry) for subjects with values of potential clinical importance will be listed, separately. Frequencies of laboratory values of potential clinical importance will be summarised.

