## **12.6 Other Safety Measures**

### **12.6.1 Vital signs**

Vital signs evaluation at each planned assessment, and change in vital signs baseline at each planned post-baseline assessment, will be summarised by actual treatment. Individual subject profiles will be plotted for each vital sign parameter (Blood Pressure and Heart Rate).

Vital signs data of potential clinical importance will be listed separately.

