### **12.6.2 ECG**

QT interval data will be presented using Bazett's (QTcB) and Fridericia's (QTcF) corrections. ECG data will be summarised by treatment and time point. Differences from baseline will be summarised by treatment and time point.

The number of subjects with a potentially clinically important ECG value will be summarised by actual treatment and time point, giving the numbers of subjects with QT, QTcB or QTcF > 450 msec, > 480 msec and > 500 msec, and the numbers of subjects with increases in QT, QTcB or QTcF from baseline of > 30 msec and > 60 msec. A supporting listing of all subjects with an ECG value of potential clinical importance and a separate listing of ECG findings classified as abnormal by the Investigator will also be provided.

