**Template T\_LB1**

Table 14.3.4.xx Summary of Laboratory Values of Potential Clinical Importance

Lab Test	Treatment	Planned Relative Time	n	Double Flags	
				HI	LD
	Treatment 1 (N=xx)				

H = Above reference interval, L = Below reference interval, I = Increase from baseline greater than pre-defined limit, D = Decrease from baseline greater than pre-defined limit

Source: Listing 16.2.xx

*Programming notes:* Continued with all tests, treatment groups and time points

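### A laboratory or ECG value taken off-schedule because an effect was suspected cannot enter the SAP's counts of potentially important results

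*SAP*

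**What the plan says.** SAP section 10.1 sets one rule for all data types: "Data collected at unscheduled time points during the study will not be used in the summaries or data analyses". The next sentence says where such values go: "They will be included in the listings". SAP section 10.3 defines no assessment windows, so the plan has no route by which an off-schedule value could be assigned to a planned time.

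Two tables count potentially important results. For laboratory data, SAP section 12.5 says: "Frequencies of laboratory values of potential clinical importance will be summarised" (Table 14.3.4, shell T_LB1). For ECG, section 12.6.2 says: "The number of subjects with a potentially clinically important ECG value will be summarised by actual treatment and time point" (Table 14.3.7.2, shell T_EG3). Both shells are laid out by "Planned Relative Time". Neither has a worst-value or any-post-dose row.

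The protocol allows extra measurements for reasons tied to a suspected effect. Section 8.12 permits added time points, with sponsor approval, for example "if it is believed that an important effect of the IMP is occurring at a time when no measurements are scheduled". Section 8.18 allows additional samples when adverse events occur.

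**The concern.** Leaving unscheduled values out of by-time means is normal practice, since those means need the same subjects measured at the same times. A count of subjects with an important value serves a different purpose: it should show whether the value ever occurred. Triggered measurements are taken because someone suspects an effect, so whether they exist depends on the outcome. Excluding them from an outlier count can only remove positives.

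The primary objective is safety and tolerability, and each cohort has only 6 active subjects, so one subject weighs heavily in any count. A reader who relies on the summary tables could see no flagged value for a treatment while a flagged value sits in a listing.

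**Working it through.** The documents give no design figure for this point, so there is none to reproduce. The check compares the rule with the table shells and the sampling schedule.

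**1. Can a triggered value reach a count?** The rule in SAP 10.1 has no exception for outlier tables. The one repeat value that enters a summary is a pre-dose laboratory repeat used as baseline (SAP 10.2), which brings in no post-dose value. Shells T_LB1 and T_EG3 offer only planned-time rows. So a post-dose value taken off-schedule in a single subject has no row.

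**2. Direction.** Let S be a subject's scheduled post-dose values and U the unscheduled ones. A subject flagged on S is also flagged on S and U together; the reverse need not hold. Hence the number ever flagged on S is at most the number ever flagged on S and U. The exclusion can lower the laboratory and ECG counts or leave them unchanged.

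**3. Consistency with other text.**
- SAP 10.4 applies the laboratory change flag to the whole course of the trial, not only to scheduled visits.
- Protocol 10.8.3 plans frequencies of potentially important laboratory values without this exclusion.
- SAP section 15, which lists changes from the protocol analysis, does not mention it.
- SAP 17.1 gives Listings 16.2.8.1 and 16.2.8.3 as the source of Table 14.3.4. Those listings will hold unscheduled flagged values and the table will not, so the two may fail to reconcile.

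**4. Where the schedule leaves gaps** (post-dose times to 24 h; protocol Table 3 for Cohort 9, Table 5 for Cohort 10):

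| | Cohort 9 | Cohort 10 |
|---|---|---|
| Safety ECG | 0.5, 1, 1.5, 2, 3, 4, 8, 12, 24 h | 1, 12, 24 h |
| Safety laboratory tests | 24 h | 24 h |

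The ECG gap from 1 to 12 h is peculiar to Cohort 10. The laboratory gap from 0 to 24 h is common to both cohorts. Cohort 10 also has glucose and insulin profile samples at 1, 12 and 24 h, but the highest glucose seen in Part 1 was at 2 h after 40 mg (protocol section 1.3), the dose that Cohort 10 repeats. A glucose sample or ECG prompted by symptoms at that time in Cohort 10 would be off-schedule.

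**5. Illustration of size.** Suppose one of 6 active subjects has a flagged value only at an unscheduled time.
- Per-subject row with unscheduled values: 1/6 = 16.7% (exact 95% CI 0.4 to 64.1%).
- Same row restricted to scheduled values: 0/6 = 0% (exact 95% CI 0 to 45.9%).

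The documents give no rate for such values. For assumed per-subject rates p, the chance that at least one of 6 is affected is 1 − (1 − p)^6:
- p = 5%: 1 − 0.95^6 = 26.5%
- p = 10%: 1 − 0.90^6 = 46.9%
- p = 20%: 1 − 0.80^6 = 73.8%

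**The case against.** The strongest reply is that nothing is lost. SAP 10.1 itself sends unscheduled values to the listings. The SAP plans dedicated listings of potentially important chemistry, haematology and ECG values, and with two cohorts of 8 every flagged value can be read individually. A test result that meets the criteria in protocol 9.2 is recorded as an adverse event, and the adverse event tables are not organised by planned time. SAP 10.2 also keeps a post-dose out-of-range laboratory value in the summaries even when its repeat is normal. No formal testing is planned.

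All of this is correct and limits the point. It does not remove it: listings give no count by treatment, not every flagged value becomes an adverse event, and the SAP 10.2 rule helps only where the scheduled value was itself out of range.

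Four stronger readings are tempting, and the documents do not support them.

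- **Every time point added under protocol 8.12 is excluded.** The SAP does not define unscheduled. A time point formally added for a whole cohort can fairly be read as scheduled. The exclusion is clear only for triggered readings in single subjects.
- **A reported rate falls from 17% to 0%.** Neither shell reports an overall per-subject rate. T_LB1 gives counts per planned time without percentages, and T_EG3 is also by planned time. The 1/6 figure belongs to the proposed row.
- **Vital signs counts are affected.** The SAP says: "Vital signs data of potential clinical importance will be listed separately". There is no frequency table to distort, so the gaps between vital signs readings do not bear on this point.
- **Extra eye visits should enter Table 14.3.10.** Protocol 8.11 says: "additional ophthalmology follow-up visit(s) may be scheduled to characterize and assess any eye-related AEs". The event that prompts the visit is already an adverse event, counted if treatment-emergent. The eye table is by time point with percentages of available results, so extra visits would add rows made up only of selected subjects.

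**Conclusion.** The point holds for the laboratory and ECG outlier tables. As written, the SAP leaves a triggered post-dose value in a single subject out of Tables 14.3.4 and 14.3.7.2, and this can only reduce what those tables show. The exposure is greatest in Cohort 10.

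The size cannot be estimated from the documents. It may be zero if no such value arises; if one does, each affected subject is one sixth of an active group. The conclusion assumes that SAP 10.1 is applied literally and that single-subject triggered readings count as unscheduled. It is a reporting gap, worth closing before database lock because safety is the primary objective and the data are already collected. It does not mean that safety data are hidden or discarded.

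**What to change.** Amend the SAP as follows.

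1. Keep the by-time-point summaries restricted to scheduled data.
2. Define unscheduled in section 10.1, stating that time points formally added for a cohort under protocol 8.12 count as scheduled.
3. Add one per-subject row, 'any post-dose, including unscheduled' (n and %), to T_LB1 and T_EG3 beside the scheduled rows, and say how it fits with the laboratory repeat rule in section 10.2.
4. List the rule in section 15.

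The cost is a few sentences and one added row in each shell, with no new data. The drawback is unequal opportunity: a subject measured more often has more chances to be flagged. Showing the new row next to the scheduled rows lets the reader see how much of a count comes from extra measurement.
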